#### 9.4 Lens Power

Lens dioptric power will be determined by each surgeon's standard of care. The subject must be targeted with the IOL power with the amount of targeted postoperative refractive error closest to 0 D based on power calculation.

Note: Preoperative corneal astigmatism must be less than 1.00 D in each eye and the predicated residual astigmatism must NOT be > 0.50 D between the two eyes.

# 9.5 Treatment Masking

This study is assessor-masked and subject-masked.

Alcon personnel (including biostatistics, masked data manager, and clinical project lead) will also be masked. All other members associated with the study (at the site and the study sponsor) are unmasked.

Alcon personnel will be masked to IOLs implanted in the eye until the 2nd interim study database lock. At the 1st interim analysis, unmasking of Alcon personnel will be limited to the subset of subjects included in the 1st interim lock as needed. Masked assessors will be masked to the IOLs implanted until the final database lock.

Subjects will be provided with implant cards by unmasked personnel upon exiting the study and will become unmasked at that time.

Masked study personnel must avoid seeking information that may compromise masking. Unmasked study personnel must not disseminate information that is potentially unmasking to any masked personnel. The masked and unmasked site personnel must coordinate all study activities as necessary to protect masking and minimize bias during the study.

# 9.5 Accountability Procedures

Upon receipt of IPs, the investigator or delegate must conduct an inventory of all lenses by serial number, complete study-specific confirmation of receipt procedures as described in the MOP and retain any required documentation in the investigator's clinical study records. Throughout the study, the investigator or delegate must maintain records of IP use for each subject. This record must be made available to the study monitor for the purposes of verifying the accounting of IP supplies. Any discrepancies and/or deficiencies between the observed disposition and the written account must be recorded along with an explanation. All IPs sent to the investigator must be accounted for by study sponsor personnel, and in no case be used in an unauthorized manner.

Refer to Section 11 of this protocol for additional information on the reporting of device deficiencies and to the MOP for information on return of investigational products associated with these events.

The investigator is responsible for proper disposition of all unused IPs at the conclusion of the study, according to the instructions provided in the MOP.

### 9.6 Changes to Concomitant Medications, Treatments/Procedures

### 9.6.1 Changes to Concomitant Medications

After the subject is enrolled into the study, the investigator must instruct the subject to notify the study site about:

- Any new medications
- Alterations in dose or dose schedules for current medications,
- Any medical procedure or hospitalization that occurred or is planned,
- Any nondrug therapies (including physical therapy and blood transfusions),

The investigator must document this information in the subject's case history source documents.

# 9.6.2 Changes to Treatments/Procedures

In the event an intraoperative exclusion criterion is met during cataract surgery, take appropriate action as described in Table 9-3. The table includes, but is not limited to, the most common or likely complications.

Table 9-3 Procedural Complications

Treatment/Procedure Complication	Precaution(s) and Action(s) to be taken	Subject Status
One or more intraoperative	Do not implant the study	Discontinue subject per Section
exclusion criteria met during 1 st eye surgery; IP did not touch the eye.	IOL. Implant another suitable nonstudy lens per standard of care.	10.4.2.
One or more intraoperative exclusion criteria met during 1 st eye surgery; IP touched the eye.	Do not implant the study IOL. Implant another suitable nonstudy lens per standard of care.	Encourage the subject to remain in the study so as to continue to perform safety assessments only in the 1 st eye, per Section 10.4.3.

Treatment/Procedure Precaution(s) and Complication Action(s) to be take		Subject Status	
		Do not implant the study IOL in the 2 nd eye.	
One or more intraoperative exclusion criteria met during 2 nd eye surgery; IP did not touch the eye.	Do not implant the study IOL. Implant another suitable nonstudy lens per standard of care.	Continue to follow the subject for all safety assessments in the 1 st eye implanted with the study IOL.  Do not perform any assessments on the 2 nd eye.	
One or more intraoperative exclusion criteria met during 2 nd eye surgery; IP touched the eye.	Do not implant the study IOL. Implant another suitable nonstudy lens per standard of care.	Continue to follow the subject for all safety assessments in the 1 st eye, implanted with the study IOL.  Continue to perform safety assessments only on the 2 nd eye, per Section 10.4.3.	

NOTE: A nonstudy lens is defined as a lens that the clinic has procured on its own (all lenses provided by Alcon for this study (for both the test group and comparator group) are considered in the category of 'study lens').

#### 10 STUDY PROCEDURES AND ASSESSMENTS

This section describes the procedures and assessments for this clinical study.

Prescreening is highly suggested for this study. A prescreening log may be provided to the sites, as needed.

There are 9 study Visits (including the screening visit) in this study.

Visit 0 is the screening visit. Informed consent procedures as well as eligibility are performed at this visit. Additionally,

- Visit 00 is the first eye operative visit,
- Visit 00A is the second eye operative visit,

- Visit 1 (1 Day) is Day 1 to Day 2 post 1st eye surgery,
- Visit 1A (1 Day) is Day 1 to Day 2 post 2nd eye surgery,
- Visit 2 (1 Week) is Day 7 to Day 14 post 1st eye surgery,
- Visit 2A (1 Week) is Day 7 to Day 14 post 2nd eye surgery,
- Visit 3A (2 month) is Day 45 to Day 70 post 2nd eye surgery,
- Visit 4A (6 month) is Day 180 to Day 210 post 2nd eye surgery.

If necessary, Visit 3A (2 months) may be completed over 2 days within a two week period, and must be completed within the specified window.

Status: Approved, Version: 2.0

Approved Date: 18 Mar 2025

# 10.1 Informed Consent and Screening

The investigator or delegate must explain the purpose and nature of the study, and have the subject read, sign, and date the IRB/IEC-approved informed consent document. The subject must sign the ICF BEFORE any study-specific procedures or assessments can be performed, including study-specific screening procedures. Additionally, have the individual obtaining consent from the subject and a witness, if applicable, sign and date the informed consent document.

The investigator or delegate must provide a copy of the signed document to the subject and place the original signed document in the subject's chart, or provide documentation as required by local regulations.

# 10.2 Description of Study Procedures and Assessments

Study-specific procedures and assessments described here may include standard of care; other standard of care procedures performed in the clinical management of the subject are not excluded.

NOTE: Historical data collected prior to informed consent and within 60 days of Screening, may be used if collected per study requirements.

Detailed descriptions of assessments and procedures are provided in the MOP. The investigator is responsible for ensuring responsibilities for all procedures and assessments are delegated to appropriately qualified site personnel.

### 10.2.1 Demographics: Entry Criteria

Obtain demographic information including age, race, ethnicity, and sex.

# 10.2.2 Medical History and Concomitant Medications: Entry Criteria

Medical history and concomitant medications will be collected in the eCRF as outlined in the MOP.

# 10.2.3 Urine Pregnancy: Entry Criteria

Perform urine pregnancy test according to the manufacturer's procedure on female subjects of childbearing potential.

# 10.2.4 Inclusion/Exclusion Criteria: Entry Criteria

Determine if subject meets entry criteria as outlined in Section 8. Subjects not meeting entry criteria are screen failures and should not continue in the study.

NOTE: Determinations related to entry criteria must be made by medically qualified study staff.

For subjects meeting entry criteria, refer to Section 9.3 for details on treatment assignment.

# 10.2.5 Keratometry, Axial Length, and Anterior Chamber Depth: Entry Criteria/

Measure keratometry, ACD, and AL according to the investigator's standard of care for each eye.

# 10.2.6 Target Residual Refractive Error: Entry Criteria/

Record target residual refractive error for each eye.

The targeted postoperative residual refractive error for lens selection must be closest to 0 D based on power calculation.

# 10.2.7 Predicted Residual Astigmatism: Entry Criteria

Record predicted residual astigmatism for each eye. The use of a IOL Toric calculator is required.

Incisions to reduce astigmatism during surgery are allowed in this study and must also be taken into account when calculating predicted residual astigmatism.

A subject with predicted residual astigmatism of > 0.50 D between the two eyes should not be enrolled in the study.

# 10.2.8 Slit Lamp Biomicroscopy: Safety Assessment

Slit lamp examination must be performed in both eyes. Record any slit lamp findings, any **IOL observations, any subjective PCO.** This assessment must be performed by medically qualified study staff.

# 10.2.9 Intraocular Pressure: Safety Assessment

Perform tonometry assessment in each eye according to the to the investigator's standard of care. Record IOP results.

# 10.2.10 Dilated Fundus: Entry Criteria/Safety Assessment

Dilated fundus examination includes ophthalmoscopic assessments of the vitreous, retina, macula, choroid, and optic nerve of both eyes. This assessment must be performed by medically qualified study staff.

# 10.2.11 Administration of Treatment (Cataract Surgery): Safety Assessment

Perform cataract surgery in alignment with each subject's assigned treatment from randomization. In both sub-studies, the 1st operative eye is defined as the eye with the worse BCDVA at Screening (Visit 0). If the BCDVA is the same in both eyes, the right eye (OD) will be identified as the 1st operative eye.

# 10.2.15 Monocular Photopic Best Corrected Distance Visual Acuity: Effectiveness Assessment at 4 m: Effectiveness Assessment

Measure monocular photopic ETDRS BCDVA at 4 m in each eye. This assessment must be performed by delegated trained masked assessor only.

# 10.2.30 Adverse Event Collection: Safety Assessment

Assess and record any AEs that are observed or reported since the previous visit, including those associated with changes in concomitant medication dosing.

Note: AEs must be recorded for all enrolled subjects from the time of signature of informed consent form, regardless of subject enrollment status (screen failure or randomized).

# 10.2.31 Device Deficiencies: Safety Assessment

Assess and record any device deficiencies that are reported or observed since the previous visit. Requirements for reporting device deficiencies in the study can be found in Section 11.

Note: Device deficiencies must be recorded for all enrolled subjects from the time of signature of informed consent form, regardless of subject enrollment status (screen failure or randomized).

# 10.2.32 IOL Observations: Safety Assessment

Document any observations related to the IOL (e.g., haze, discoloration).

# 10.2.33 Subjective PCO: Safety Assessment

Assess and document presence of posterior capsule opacification (PCO).

### 10.2.34 Nd: YAG Capsulotomy: Safety Assessment

If a posterior capsulotomy (i.e., YAG laser treatment) has been performed since last visit, document the treatment including treatment date, eye, and size of the capsulotomy.

# 10.2.35 SSI: Safety Assessment

Document and report any SSIs (e.g., IOL repositioning) as an SAE.

#### 10.3 Unscheduled Visits

If a subject visit occurs between any regularly scheduled visit and the visit is conducted by study personnel, this visit must be documented as an Unscheduled Visit. If the subject seeks medical attention outside the clinic (for example, at an emergency room) or at the clinic but is seen by nonstudy personnel, the investigator is to capture AE-related information on the AE form upon becoming aware.

During all unscheduled visits, the investigator must conduct the following procedures:

- Collect AE information
- Record changes in medical condition or concomitant medication

The investigator may perform optional study assessment as outlined in Table 3-1, if clinically indicated.

The investigator may perform additional non-study procedures for proper diagnosis and treatment of the subject. The investigator must document this information in the subject's case history source documents.

# **10.4 Discontinued Subjects**

#### 10.4.1 Screen Failures

Subjects who were excluded from the study after signing the informed consent form and prior to randomization are considered screen failures. Subjects who are deemed no longer eligible to be implanted with a study lens after randomization (due to intraoperative exclusions or other noted issues) will be withdrawn from the study.

The investigator must document the reason for screen failure or withdrawal in the subject's case history source documents.

Subject numbers must not be re-used.

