# 7.3 Rationale for Duration of Treatment/Follow-Up

All subjects will be followed for approximately 6 months postoperatively. This period will allow sufficient subject recovery from surgery and stability of visual outcomes. Additionally, this postoperative period will ensure adequate evaluation of the primary endpoints being assessed at the 2-month (Visit 3A) postoperative visit, and to adequately assess device safety.

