#### 10.4.2 Discontinuations

Discontinued subjects are individuals who voluntarily withdraw or are withdrawn from the study by the investigator after exposure to investigational product.

NOTE: Subjects not implanted at the time of surgery (1st operative eye) and the study IOL **did not** touch the eye must be captured as withdrawn.

Subject numbers of discontinued subjects must not be re-used for another subject (i.e., subject replacement is not allowed).

Subjects may discontinue from study or study treatment at any time for any reason. Subjects may also be discontinued from study treatment at any time if, in the opinion of the investigator, continued treatment poses a risk to their health.

The investigator must document the reason for study or treatment discontinuation in the subject's case history source documents.

To ensure the safety of all subjects who discontinue early, investigators must assess each subject and, if necessary, advise them of any therapies and/or medical procedures that may be needed to maintain their health.

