# 10.4.3 Subjects with Aborted Implantation and Explanted IOL(s)

Implantation may be attempted twice. After two aborted attempts to implant, meaning the investigational product touched the eye, the eye must be implanted with a nonstudy provided IOL. Refer to Section 9.6.2 for additional information.

If the IOL implantation is attempted and aborted due to device deficiency, then a device deficiency form must be completed and the IOL must be returned to the study sponsor in appropriate safe packaging.

In case an explant is performed: the explanted eye will be followed for safety as routine standard of care for explants of approved IOLs.

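### The withdrawal sentence in Protocol 10.4.1 is too broad: it contradicts Table 9-3 and can be read to withdraw a subject whose first eye already holds a study lens

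*Protocol*

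**What the plan says.** Protocol 10.4.1 (Screen Failures) first defines screen failures as subjects excluded between consent and randomization. It then adds a rule for randomized subjects: those judged no longer eligible to receive a study lens "after randomization (due to intraoperative exclusions or other noted issues) will be withdrawn from the study". The rule does not mention which eye is concerned or whether the product touched it.

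Protocol 9.6.2 gives a separate rule for exclusions met in the operating room: "In the event an intraoperative exclusion criterion is met during cataract surgery, take appropriate action as described in Table 9-3". Table 9-3 has four rows. Only row 1 (first eye, no product contact) ends participation. For row 2 (first eye, product contact) the instruction is: "Encourage the subject to remain in the study so as to continue to perform safety assessments only in the" first eye. For rows 3 and 4 (second eye, without and with contact) it is: "Continue to follow the subject for all safety assessments in the" first eye, which holds the study lens. Row 4 adds safety assessments of the second eye. The text above the table says that its list of complications is not exhaustive.

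Protocol 10.4.2 notes that subjects whose first eye was neither implanted nor touched "must be captured as withdrawn". It also separates leaving the study from stopping treatment: "Subjects may discontinue from study or study treatment at any time for any reason". Protocol 10.4.3, on aborted implantations and explants, ends its first paragraph with "Refer to Section 9.6.2 for additional information".

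**The concern.** Randomization comes before first-eye surgery (Table 3-1, footnote j), so a rule that applies after randomization spans both operations. Taken at its words, 10.4.1 withdraws subjects whom Table 9-3 keeps under observation. It names intraoperative exclusions, which are the very events that Table 9-3 governs.

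The case that matters more is one that Table 9-3 does not list. A subject has a study lens in the first eye, and the second eye is then found ineligible before its surgery. Besides intraoperative exclusions, 10.4.1 names other issues in general terms, so its words can reach this case. Table 3-1 marks the inclusion and exclusion criteria at Visit 00A, and exclusion 9 (a confounding or risk-raising comorbidity) is one that could arise between the two operations. If the subject were withdrawn, a permanently implanted eye in the Safety Set would lose its later scheduled safety examinations. Rows 3 and 4 keep a subject in the same clinical position under follow-up.

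**Working it through.** The plan gives no figure on this point. The check is a comparison of texts, followed by a count of what the uncovered case would lose.

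**1. Dispositions side by side**

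| Situation | 10.4.1 as worded | Table 9-3 |
|---|---|---|
| First eye, no contact (row 1) | Withdraw | Discontinue: agrees |
| First eye, contact (row 2) | Withdraw | Encourage to stay, safety only: conflicts |
| Second eye, no contact (row 3) | Withdraw | Follow first eye: conflicts |
| Second eye, contact (row 4) | Withdraw | Follow first eye, and second eye for safety: conflicts |
| Second eye ineligible before surgery | Can be read as withdraw | No express row |

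**2. Examinations lost in the last situation**

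Inputs from Table 3-1: postoperative visits 1, 2, 1A, 2A, 3A and 4A (six); slit lamp at all six; intraocular pressure at all six; postoperative dilated fundus examination at Visit 4A only. Sections 10.2.8 to 10.2.10 require these examinations in both eyes. First-eye total: 6 + 6 + 1 = 13.

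Two points are uncertain. Visit 2 falls on days 7 to 14 after first-eye surgery, and second-eye surgery is recommended in the same window, so Visit 2 may or may not have taken place. Footnote f limits some assessment to the eye relevant to the visit, but its marker is not visible in the public table. The table therefore also shows the count with Visits 1A and 2A taken as second-eye visits only (4 + 4 + 1 = 9 first-eye examinations).

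| Assumption | Lost | Share |
|---|---|---|
| Both eyes at every visit, Visit 2 done | 4 + 4 + 1 = 9 of 13 | 69% |
| Both eyes at every visit, Visit 2 not done | 5 + 5 + 1 = 11 of 13 | 85% |
| Visits 1A and 2A second eye only, Visit 2 done | 2 + 2 + 1 = 5 of 9 | 56% |
| Visits 1A and 2A second eye only, Visit 2 not done | 3 + 3 + 1 = 7 of 9 | 78% |

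Under every assumption the single scheduled postoperative fundus examination is lost.

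**3. Length of first-eye follow-up**

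Footnote c recommends, but does not require, 7 to 14 days between operations. Visit 4A is 180 to 210 days after the second. Planned first-eye follow-up is therefore 7 + 180 = 187 to 14 + 210 = 224 days. A subject withdrawn on the day of Visit 00A has 7 to 14 days, which is between 7/(7 + 210) = 3.2% and 14/(14 + 180) = 7.2% of the plan.

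**4. Effect on the analyses**

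The All-Implanted Analysis Set needs both lenses successfully implanted (Protocol 12.2, SAP 2.1). This subject is outside it whether withdrawn or followed, so the primary sample size and power do not change. Safety Set membership follows from attempted implantation of an eye, so it does not change either. Each such subject is 1/66 = 1.5% of a sub-study, or 1/132 = 0.8% of the trial.

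**The case against.** The strongest defence is that the protocol, read as a whole, already gives the right answer. Section 9.6.2 is the specific rule for events during surgery and 10.4.3 points back to it. The 10.4.1 sentence stands under a heading about screen failures and speaks of a subject and *a study lens*, not of an eye. Section 10.4.2 deals with subjects who leave after exposure. On that reading 10.4.1 concerns only subjects never exposed, for whom it agrees with row 1. For a second eye that fails before surgery, row 3 is a close analogue, and the table says that its list is not exhaustive.

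Much of this stands. A reader might infer that sites would wrongly withdraw subjects after intraoperative exclusions. The documents do not support that, because 9.6.2 tells sites what to do. The uncovered case also rests on an arguable reading of 10.4.1, and on a Visit 00A eligibility mark whose scope is not stated: it may cover all criteria or only the intraoperative ones, 13 to 16.

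Two further inferences should be set aside. The 10.4.2 note does not confine withdrawal to an untouched first eye: it says that such subjects are captured as withdrawn, not that only they are. Section 7.3 ("All subjects will be followed for approximately 6 months postoperatively") explains the planned duration. Any withdrawal rule would sit awkwardly beside it, so it proves nothing here.

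The defence does not remove the breadth of the sentence itself. Nothing in it limits it to unexposed subjects, it names intraoperative exclusions, and row 3 is by its terms about an exclusion met during surgery. An investigator has to reason by analogy where one line of text would settle the matter.

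**Conclusion.** The sentence is wrong as worded, with low severity. It contradicts rows 2 to 4 of Table 9-3, although sites would probably resolve those cases correctly. The remaining risk is confined to a subject with an implanted first eye whose second eye becomes ineligible before its surgery. If 10.4.1 is read to withdraw that subject, the implanted eye loses between 5 of 9 and 11 of 13 scheduled examinations, depending on the assumptions shown above, and always the Visit 4A fundus examination.

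The documents give no frequency and none is assumed here. Several provisions soften the loss: 10.4.2 requires an assessment of subjects who discontinue early, 11.8 requires continuing care and allows later adverse event information, and events up to study exit are reported. None of them restores the scheduled examinations.

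A reader might infer a threat to the primary result or to the composition of the Safety Set. Neither follows from the analysis set definitions, and safety is analysed descriptively without hypotheses.

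**What to change.** Three changes to the protocol:

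- In 10.4.1, limit the withdrawal sentence to randomized subjects with no study lens implanted in, and no product contact with, either eye.
- Refer all other cases to Table 9-3 and 10.4.3.
- Extend row 3 of Table 9-3 to a second eye found ineligible before its surgery, so that safety follow-up of the implanted first eye continues, with the 2-month and 6-month visits timed from first-eye surgery.

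The timing clause is needed because Visits 3A and 4A are dated from second-eye surgery, which would not take place as a study procedure. With it, first-eye follow-up runs to 180 to 210 days. The two retained visits keep two slit lamp examinations, two pressure measurements and the fundus examination.

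The cost is a short protocol amendment, which may need IRB/IEC approval under Section 4 unless it counts as administrative, and notice to sites. The SAP needs a one-line visit-assignment note, because SAP Table 10-1 dates these visits from Visit 00A and the pressure, slit lamp and fundus summaries (SAP 5.3.3, 5.3.4, 5.3.8) are by visit. No subjects and no new procedures are added.
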